15. APPENDIX D: BASELINE VISUAL ANALOG SCALE QUESTIONS

For these questions we are going to ask you to make a mark on a line.

[figure not shown]
For example, let's say you are asked how much you like Oreo cookies:

How much do you like Oreo cookies? (make a mark on the line)

[figure not shown]

You answer the question by making a mark on the line according to how much you like or dislike Oreo cookies.

[figure not shown]
If you liked Oreo cookies a lot, then you might make a mark on the line like so:

If you liked Oreo cookies more than life itself(!), then you might make a mark on the line like so:

If you hated Oreo cookies, then you might make a mark like so:

If you thought Oreo cookies were just "OK," then you might make a mark like so:

The idea is that if you like Oreo cookies, you make a mark on the line closer to the phrase "very much;" the closer you make the mark, the more you are saying you like Oreo cookies. If you don't like Oreo cookies, you make a mark on the line closer to the phrase "very little;" the closer you make the mark, the more you are saying you don't like Oreo cookies.

PLEASE TURN TO THE NEXT PAGE AND ANSWER THE QUESTIONS.

Make a mark on the line to indicate:

When you think of your typical period, how heavy is your bleeding?

no
flow

heaviest flow I
ever experienced

When you think of your typical period, how acceptable is your bleeding?

not
acceptable

completely
acceptable

When you think of your typical period, how much cramping pain do you have?

no
pain

worst pain I
ever experienced

When you think of your typical period, how much does it interfere with your ability to do daily activities?

no
effect

I cannot do any
daily activities

When you think of your typical period, how much does it affect your ability to sleep?

no
effect

I do not get
any sleep

Date

[figure not shown]
Subject's signature

16. APPENDIX E: 3-MONTH AND 6-MONTH VISUAL ANALOG SCALE QUESTIONS

For these questions we are going to ask you to make a mark on a line.

[figure not shown]
For example, let's say you are asked how much you like Oreo cookies:

How much do you like Oreo cookies? (make a mark on the line)

[figure not shown]

You answer the question by making a mark on the line according to how much you like or dislike Oreo cookies.

[figure not shown]
If you liked Oreo cookies a lot, then you might make a mark on the line like so:

If you liked Oreo cookies more than life itself(!), then you might make a mark on the line like so:

If you hated Oreo cookies, then you might make a mark like so:

If you thought Oreo cookies were just "OK," then you might make a mark like so:

The idea is that if you like Oreo cookies, you make a mark on the line closer to the phrase "very much;" the closer you make the mark, the more you are saying you like Oreo cookies. If you don't like Oreo cookies, you make a mark on the line closer to the phrase "very little;" the closer you make the mark, the more you are saying you don't like Oreo cookies.

PLEASE TURN TO THE NEXT PAGE AND ANSWER THE QUESTIONS.

Make a mark on the line to indicate:

When you think of the bleeding you have had over the last 4 weeks, how heavy was your bleeding?

no flow _____ heaviest flow I ever experienced

When you think of the bleeding you have had over the last 4 weeks, how acceptable was your bleeding?

not acceptable _____ completely acceptable

When you think of the cramping pain you have had over the last 4 weeks, how much cramping pain did you have?

no pain _____ worst pain I ever experienced

When you think of the bleeding and cramping you have had over the last 4 weeks, how much did it interfere with your ability to do daily activities?

no effect _____ I cannot do any daily activities

When you think of the bleeding and cramping you have had over the last 4 weeks, how much did it affect your ability to sleep?

no effect _____ I do not get any sleep

Date

Subject's signature

17. APPENDIX F: MANAGEMENT OF PREGNANCY

Among women who conceive with an IUS *in situ*, the spontaneous abortion rate is two-fold higher than that of the general obstetric population. A retained IUS also increases the risk of several late gestational adverse maternal and neonatal outcomes; this risk is reduced, but not eliminated, with early removal of the IUS.

For any subject who has a positive urine pregnancy test, the pregnancy should be confirmed by ultrasonography and serum hCG testing. The location of the pregnancy must be determined (intrauterine or extrauterine) using ultrasonography. Determine the location of the IUS using physical examination, ultrasonography and/or radiography as appropriate.

1. Management of intrauterine pregnancy with IUS in place

The following steps may be considered in the evaluation and management of intrauterine pregnancy in a subject with an IUS *in situ*:

- First trimester intrauterine pregnancy:
 - If the IUS strings are visible on speculum examination, remove the IUS to decrease the risk of subsequent miscarriage and infection. Antibiotics are unnecessary.
 - If the strings are not visible and the patient wishes to continue the pregnancy, remove the IUS under ultrasound guidance using an alligator forceps or an IUS hook. Removal can also be attempted by hysteroscopy. Data on hysteroscopic removal of IUS in early pregnancy are limited; therefore, it is not clear whether this technique poses greater or lesser risk of pregnancy loss than instrument removal under ultrasound guidance. Antibiotic prophylaxis is recommended when instrument removals are performed during pregnancy, including when IUS removal is to be followed by pregnancy termination (see below). The IUS may be left *in situ* if findings on ultrasound examination suggest removal will be difficult or disrupt the pregnancy (e.g., IUS embedded in the placenta or membranes).
 - If the woman desires pregnancy termination, IUS removal can be performed at the time of the termination. Manual or electric vacuum aspiration or an instrument such as an IUS hook, alligator forceps, ring forceps, or ovum forceps can be used to remove the IUS.

- In the setting of spontaneous abortion with IUS in place, it is recommended to remove the IUS and prescribe antibiotics (e.g., doxycycline 100 mg twice a day or ampicillin 500 mg four times a day for seven days).
- Second trimester pregnancy —Counsel subject if the IUS remains *in situ*, that there is an increased risk of preterm labor and delivery (fourfold increase), second trimester fetal loss, and infection, but no proven increase in risk of birth defects. Removal of the IUS may cause rupture of membranes, bleeding, pregnancy loss, or fetal trauma; however, if the IUS is removed or expelled without complications, there is no increased risk of miscarriage.
 - Given this information, for pregnancies after 12 weeks, consider removing the IUS by pulling on the strings if the strings are visible and removal is unlikely to disrupt the placenta or membranes (based upon ultrasound localization of the IUS and placenta).
 - If the strings are not visible in the early second trimester, the IUS may be removed under ultrasound guidance if removal appears feasible, the IUS is not located behind the placenta, and it does not appear to be incorporated into the gestational sac. In particular, ultrasound guided removal is recommended in these cases if the IUS is in the lower uterine segment. If the IUS appears embedded in the placenta, located behind the placenta, or protrudes into the gestational sac, we suggest leaving the IUS *in situ*.
 - In the later second trimester, if the strings are not visible, the IUS should be left in place. The subject should be counseled that her risk of spontaneous abortion and premature delivery is increased relative to women whose IUSs may be easily removed.

2. Management of intrauterine pregnancy with extrauterine IUS

- If the IUS was expelled, the pregnancy should be managed as any other intrauterine pregnancy.
- If the IUS is extrauterine (perforation), the pregnancy should be managed without removal of the IUS until after the pregnancy is complete or, if applicable, at the time of cesarean delivery.

3. Management of extrauterine pregnancy

- Management should be performed within the local standard of care for the extrauterine pregnancy.
- If the IUS is intrauterine, the IUS should be removed and the subject discontinued from the study following appropriate safety follow-up.

18. APPENDIX G: MANAGEMENT OF IUS ISSUES

1. Difficult Insertion

If insertion is difficult because the cervix cannot be properly visualized then the subject should have been excluded prior to randomization.

- If insertion is difficult because the uterus cannot be instrumented, the following measures are allowed:
 - Use of cervical anesthesia to make sounding and manipulation more tolerable
 - Use of rigid dilators to dilate the cervix if needed to allow passage of the sound.
If needed, a lacrimal duct probe or os finder may be used to start dilation.
 - Abdominal ultrasound guidance during dilation and/or insertion.

If the uterus still cannot be appropriately instrumented after the above measures are taken, or the uterus sounds to less than 5.5cm, then the subject should be considered an insertion failure and discontinued from the study. No further follow-up or visits are required.

2. Perforation

- Perforation may occur during insertion. The risk of perforation is increased in women with fixed retroverted uteri, during lactation, and postpartum. If during or after insertion there is clinical concern or exceptional pain or bleeding, appropriate and timely measures and assessments, such as ultrasound, should be performed to exclude perforation.
- Perforation or penetration of the uterine wall or cervix may occur during insertion although the perforation may not be detected until sometime later. The IUS must be located and removed; surgery may be required. Delayed detection of perforation may result in migration outside the uterine cavity, adhesions, peritonitis, intestinal perforations, intestinal obstruction, abscesses and erosion of adjacent viscera. Ensure a radiographic image of the entire abdomen is obtained to ensure the IUS hasn't migrated.
- If recognized and the IUS is intra-abdominal, a laparoscopy should be performed by a clinician experienced in such procedures to remove the IUS. Typically, minimal adhesions are present with intra-abdominal IUSs. If necessary, a laparotomy should be performed.

If the IUS is partially into or through the myometrium, it is reasonable to attempt removal with transcervical instrumentation. Initial attempts should be performed under ultrasound

guidance using an Alligator forceps (or similar instrument). If unsuccessful, attempts via hysteroscopy should be made before proceeding to laparoscopy.

3. Missing Strings

The site should check for the IUS strings by palpation or direct visualization at each study visit. Ultrasound examination to verify the IUS is in place cannot substitute for checking the strings. If the strings are not evident on exam follow these steps, moving to the next one if unsuccessful:

- Use endobrush in cervical canal to attempt to tease down string.
- Perform a transvaginal ultrasound examination to locate the IUS. If the IUS is confirmed to be present in the uterus and the strings are missing, then transvaginal ultrasonography should be performed at all follow-up visits to confirm presence of the IUS.
- Obtain a flat plate abdominal x-ray to check if the IUS is within the abdomen.
 - If it is not visible on abdominal x-ray, the case will be considered a spontaneous expulsion.
 - If it is visible on x-ray, but not within the uterus on ultrasound, the case will be considered a perforation. The patient should then be referred, as necessary, for IUS removal by laparoscopy or laparotomy, and for any other necessary care.
- Subjects who experience IUS expulsion may have another study IUS inserted; only one replacement IUS is allowed per subject. Replacement can occur only if all of the following conditions are met:
 - Reinsertion occurs no more than 14 days after the expulsion;
 - Reinsertion occurs at least 7 days prior to treatment Cycle 3 or Cycle 6;
 - Reinsertion cannot occur during treatment Cycle 3 or Cycle 6;
 - Pregnancy can reasonably be excluded.

4. Partial Expulsion

Defined as visual evidence of the lower portion of the IUS stem protruding through the cervical os OR evidence of increased bleeding and/or cramping complaints with the presence of the IUS in the lower uterine segment. The system can be expelled from the uterine cavity without the woman noticing it, resulting in the loss of contraceptive protection. As menstrual flow typically decreases after the first 3 to 6 months of IUS use, an increase of menstrual flow may be indicative of an expulsion.

- The IUS should be removed as soon as possible.
- Subjects who experience a partial IUS expulsion may have another study IUS inserted (see criteria in #3 above)

5. Infection

- Patients must be taught to recognize and report to their physician promptly any symptoms of pelvic inflammatory disease. These symptoms include development of menstrual disorders (prolonged or heavy bleeding), unusual vaginal discharge, abdominal or pelvic pain or tenderness, dyspareunia, chills, and fever. Following a diagnosis of PID, or suspected PID, bacteriologic specimens should be obtained and antibiotic therapy should be initiated promptly.
- Any woman treated by a medical professional for uterine infection/PID will be considered to have that diagnosis. At a minimum, uterine tenderness must be present. The IUS should not be removed when such a diagnosis is made unless the infection is refractory to antibiotic therapy or the subject has a pelvic abscess or sepsis.

6. Difficult Removal

If the IUS cannot be removed by pulling on the strings, first make sure the clinician is certain the IUS is still in the uterus. Embedment can result in difficult removal and, in some cases surgical removal may be necessary. An embedded IUS should be removed. Embedment may decrease contraceptive effectiveness and result in pregnancy. Once certain the IUS is in the uterus, consider any of the following options alone or in combination:

- Abdominal ultrasound guidance
- Cervical anesthesia to make manipulation more tolerable
- IUD thread retriever
- Alligator forceps (or comparable instrument)

If the IUS still cannot be removed in an office setting using the above techniques, hysteroscopic evaluation for removal should be performed.

After removal of the IUS, verify that the system is intact. If the system is not intact, any missing parts must be located and removed. If removal of missing parts cannot be completed in the office, contact the Medical Monitor before attempting any other procedures. As a reminder, all removed IUSs should be collected and stored in a temperature controlled freezer.

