6.8.2 Enrollment Procedures

- Prior to IUS insertion attempt:
 - Review medical history changes since the prior visit
 - Review medication history changes since the prior visit
 - Obtain blood pressure, pulse and weight
 - Obtain high sensitivity urine pregnancy test (if test is positive then subject is a screen failure)
 - Confirm eligibility criteria
 - Subject completion of Baseline VAS questionnaire (Appendix D)
 - Collect venous blood sample for hemoglobin, hematocrit, ferritin
 - Perform pelvic exam (repeat exam if second insertion attempt on separate day)
 - Perform Chlamydia and gonorrhea testing if the subject has a new sexual partner since the Screening Phase Visit 1

- IUS insertion can occur without test results
- Women with positive tests should be contacted and receive treatment as soon as possible without waiting for the next study clinic visit
- If a pelvic exam demonstrates signs of acute cervical or uterine infection, provide appropriate antibiotic treatment and postpone the insertion attempt until subject is considered clinically cured for at least 7 days
- Vaginal infections (e.g., trichomaniasis, symptomatic bacterial vaginosis or symptomatic vaginal candidiasis) can be treated at the time of IUS insertion
- Insert the study IUS using the techniques described in the Investigator's Brochure
 - Up to two attempts for insertion can be made (on the same day or 30 days of each other)
 - If a second attempt is performed on a different day, repeat all steps listed under "Prior to IUS insertion attempt" except blood testing and VAS questionnaire
 - Each attempt should use a new IUS
 - If the IUS is unable to be inserted after two attempts or the uterus sounds to <5.5 cm:
 - If there are no AEs related to the insertion attempt (s), the subject will be discontinued from the study and is not required to have any subsequent study-related follow-up
 - If there are AEs related to the insertion attempt (s) the subject should be followed at appropriate intervals by clinic visit or telephone contact until the adverse event resolves or has stabilized, after which the subject can be discontinued from the study
- Evaluate for adverse events related to IUS placement procedure
- Distribute study-specific feminine hygiene products and diaries as needed
- Instruct subjects on the following

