7.14 Follow-up of Adverse Events and Serious Adverse Events

All AEs and SAEs must be followed through the Safety Follow-up, and any IUS or IUS procedure related AEs or SAEs followed until resolution, or until the condition stabilizes, or until all queries are resolved, or until the subject dies or is lost to follow-up (including withdrawal of consent). The Investigator is responsible to ensure that follow-up includes any supplemental investigations as may be indicated to elucidate as completely as practical the nature and/or causality of the AE/SAE. This may include additional laboratory tests or investigations, histopathologic examinations, or consultation with other health care professionals. Follow-up information should be submitted to the Sponsor in a timely manner as the information is obtained.

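### Appendix G waives all follow-up after a failed insertion, omitting the related-AE exception in Section 6.8.2 and the follow-up duty in Section 7.14

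*Protocol*

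**What the plan says.** Protocol Appendix G, item 1, lists the measures allowed when the uterus is hard to instrument: cervical anesthesia, rigid dilators (with a lacrimal duct probe or os finder if needed) and ultrasound guidance. If these fail, or "the uterus sounds to less than 5.5cm, then the subject should be considered an insertion failure and discontinued from the study". The item then ends: "No further follow-up or visits are required". It states no condition about AEs and gives no cross-reference.

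Protocol Section 6.8.2, the Visit 5 procedure, covers an overlapping situation: "If the IUS is unable to be inserted after two attempts or the uterus sounds to <5.5 cm". It then divides by AE status:

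- "If there are no AEs related to the insertion attempt (s), the subject will be discontinued from the study and is not required" to have later study follow-up.
- "If there are AEs related to the insertion attempt (s) the subject should be followed at appropriate intervals by clinic visit or telephone contact", and this continues "until the adverse event resolves or has stabilized, after which the subject can be discontinued from the study".

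Protocol Section 7.14 sets the general duty: "any IUS or IUS procedure related AEs or SAEs followed until resolution". Its other stopping points are stabilization, resolution of all queries, death, and loss to follow-up, which includes withdrawal of consent.

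**The concern.** Two parts of the protocol tell the site what to do after a failed insertion, and only one protects a woman who has been hurt by the procedure. Section 7.1.4 directs the reader to Appendix G for difficult insertion, so a site may well act on the appendix. If it does, it could discontinue the woman and stop contact while a procedure-related AE is still open, and the final outcome of that event might never be captured.

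The order of steps matters too. Section 6.8.2 puts follow-up before discontinuation, while Appendix G discontinues at once. Section 7.17.2 counts discontinuation at the investigator's request among its withdrawal criteria and stops data collection for anyone designated as withdrawn. On a plain reading, discontinuing first could therefore close off data on the open AE.

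**Working it through.** No arithmetic applies, because the documents give no rate of failed instrumentation, short sounding or related AEs. The check is a comparison of instructions.

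**Step 1. Compare the rules case by case.**

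| Case | Appendix G, item 1 | Section 6.8.2 | Section 7.14 |
|---|---|---|---|
| Sounds to <5.5 cm, no related AE | Discontinue, no follow-up | Discontinue, no follow-up | No related AE to follow |
| Sounds to <5.5 cm, AE related to an insertion attempt | Discontinue, no follow-up | Follow to resolution or stabilization, then discontinue | Follow |
| Sounds to <5.5 cm or cannot be instrumented, AE arising before any attempt | Discontinue, no follow-up | AE branch may not reach it on literal wording | Follow |

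The first row agrees. The second conflicts with both sections. The third conflicts with Section 7.14.

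**Step 2. Check whether Section 7.14 covers the third row.** Section 6.6 starts an insertion attempt when the inserter passes the external cervical os. It starts IUS insertion as a process earlier, at opening of the kit, and gives inability to sound the uterus as an example of that process stopping before an attempt. Sounding is thus treated as part of the procedure. Section 7.13 counts untoward events as AEs from the beginning of the insertion procedure. An AE from sounding, dilation or cervical anesthesia is then procedure-related, and Section 7.14 applies.

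**Step 3. Check whether other text restores the exception.** Nothing else in Appendix G does so for this case; item 2 covers perforation only. Section 6.11 does not clearly do so: its 7 to 10 day contact is for women whose IUS was removed, and its monthly contacts follow completion of the Treatment Phase. By contrast, Appendix F, item 3, discontinues a woman with an extrauterine pregnancy only after suitable safety follow-up, which is the kind of qualifier missing here.

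**Step 4. Check that a related AE is plausible.** Women reach the Appendix G sentence after the measures listed there have been tried. Section 7.1.16 lists risks of cervical anesthesia, among them nausea, light-headedness and, rarely, seizure.

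**Step 5. Bound the consequence.**

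- Section 6.8.2 also instructs the site at Visit 5: "Evaluate for adverse events related to IUS placement procedure". The event would be recorded, and Section 7.10.4 provides ongoing and unknown as outcome categories. What may be lost is the final outcome.
- Section 6.7.2.5 makes a woman in whom no endometrial biopsy can be obtained a screen failure. That should remove many uteri that cannot be instrumented before Visit 5.
- Every efficacy population in SAP Section 6 requires successful insertion, so these women are in none of them.

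**The case against.** The strongest reply is that the conflict with Section 6.8.2 is narrower than it looks. The AE branch there concerns events related to an insertion attempt, and under Section 6.6 an attempt has not begun when sounding fails or is short. If no attempt was made, 6.8.2 read literally reaches the same result as Appendix G. A literal clash with 6.8.2 then needs an earlier failed attempt, or failure after the inserter has passed the os. This stands. It does not remove the clash with Section 7.14, which covers procedure-related events, although reaching 7.14 depends on reading Sections 6.6 and 7.13 together.

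A second reply is that Appendix G is clinical guidance on the device, that AE follow-up is governed by Section 7, and that the sentence naturally means the remaining treatment visits fall away because no IUS is in place. It does not forbid follow-up. That is a fair account of the probable intent, and a site that also reads 6.8.2 and 7.14 would act correctly. But the sentence is unqualified, Section 7.1.4 points to it, and no rule was found saying whether body text or appendix prevails.

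A third reply is that harm requires a site to use the appendix alone and ignore the visit procedure. This limits the importance of the point but does not make the sentence correct.

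**Conclusion.** The point holds and is minor. Appendix G, item 1, omits the related-AE exception, and followed literally it ends follow-up where Section 7.14 requires it to continue and, once an insertion attempt has been made, where Section 6.8.2 does too. The effect is confined to the outcome of procedure-related AEs in women whose insertion failed. Their number is likely small but cannot be computed from the documents; the text of Section 7.1.4 that might have helped is redacted. The primary result is untouched. The conclusion for AEs arising before an attempt rests on treating sounding as part of the insertion procedure, as Section 6.6 implies.

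**What to change.** Make the closing sentence of Appendix G, item 1, conditional. Suggested content: follow-up and visits are waived unless there is an AE related to the insertion attempt or procedure; such an AE is followed until resolved or stabilized under Sections 6.8.2 and 7.14, and the subject is discontinued only after that. Naming the procedure as well as the attempt covers events that occur during sounding or dilation.

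Adding the same reference to the procedure in the two AE branches of Section 6.8.2 would be a sensible companion edit, since those branches now mention attempts only. It is not essential, because Section 7.14 already covers these events.

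The cost is one sentence of protocol wording, with no change to design, sample size or analysis.
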